11.3. Sample Size Determination

Sample size calculations were performed to estimate a) the minimum number of HCCs and b) patients with cirrhosis and number of HCC needed to detect a difference in sensitivity and specificity between nceMRI and USS. Calculations used McNemar's test for paired proportions (power 90%, type 1 error at 5%). Based on literature, we assumed nceMRI and USS sensitivity of 70-90%⁴³ and 30-50%¹⁸ respectively, and nceMRI and USS specificity of 80%⁴³ and 90%¹⁸ respectively. The calculations suggest that in most scenarios, 50 HCCs and 200 controls would be sufficient to identify a difference in sensitivity/specificity.

Sensitivity		Ultrasound		
		se=30%	se=40%	se=50%
	se=70%	31	54	116
nceMRI	se=80%	21	30	50
	se=90%	14	19	27
Specificity		sp=90%	sp=95%	sp=98%
	sp=80%	244	96	61
nceMRI	sp=90%	NA	530	173
	sp=98%	173	2	NA

Table 2. Minimum number of participants required to demonstrate a statistically significant difference

 in sensitivity/specificity

To observe at least 50 HCCs, the cohort will be enriched with people with a risk of HCC of at least 3% per year (see section 9.4 also). This 3% per year threshold is derived from risk distribution observed among the first 1500 patients recruited to the Pearl cohort. Assuming there will be 2150 participants in Pearl at the time of AMULET inception, and assuming we will continue to see the same risk distribution in the
latter recruited patients as for the first 1500 patients, we determined that selecting patients with a 3year risk of >9% would give rise to 50 HCCs plus ~250-300 controls with liver cirrhosis and no HCC.

Figure 4. HCC risk distribution in Pearl – expected number of HCCs and non HCCs at a >3% annual HCC risk threshold

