Design and Methods: We will recruit 300 people at higher risk of developing liver cancer because of cirrhosis. Study participants will have an ultrasound scan every 6 months as they would in their standard clinical care and an additional 6 monthly non-contrast MRI scan for 30 months (6 visits). If the ultrasound or non-contrast MRI raises concern for a possible liver cancer, an MRI scan with contrast (with dye injection) will be done for definitive diagnosis. All participants will have an MRI with contrast at the end of 30 months to ensure that no cancers were missed. Participants will be asked to complete questionnaires to measure quality of life, anxiety, and their experience of MRI and ultrasound scans and data will be collected from their medical notes. We will compare the number of liver cancers detected by ultrasound to the number detected by the non-contrast MRI scans.

Follow up data will be collected from NHS England, the NHS Central Register for Scotland and other patient registries for up to 10 years after the last study MRI scan to determine the long-term outcomes of participants.

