• The PRIUS project from Korea (NCT01446666) was a prospective study comparing the diagnostic accuracy of full-length contrast-enhanced MRI and USS²⁶ over 3 rounds of surveillance in patients with an annual HCC risk of $\geq 5\%$. Two post-hoc analyses of this study have been published. The first showed that the MRI sequences acquired before the administration of contrast agent (DWI (b-values: 0, 50, 500 s/mm²) and T2WI (heavily weighted using long TE and non-fat suppressed (NFS)) had superior sensitivity (79% vs 28%) and similar specificity (98% vs 95%) to USS¹⁷. The second showed that a simulated abbreviated contrast-enhanced MRI protocol using subsets from the full PRIUS MRI protocol had similar sensitivity to nceMRI (90.7% vs 86.0%; p=0.56) and both were superior to the sensitivity of US (27.9%; p < 0.001)²³. These findings support our choice to use a nceMRI protocol, as the addition of contrast in this setting does not appear to improve performance. The MRI protocol in this study is similar to the one we will be using for our study.

• A prospective study in Australia, examined only DWI MRI (b-values: 100, 400, 800 s/mm²) against USS²⁷ in 192 patients and found higher sensitivity for USS (100% vs 83%). The MRI protocol used in this study was limited just to DWI and that makes it less relevant to our study where we include additional sequences. Furthermore, this study was limited by high attrition rate.

• The MAGNUS-HCC project from Korea compared annual non-contrast enhanced MRI to 6 monthly USS as surveillance in people with cirrhosis and an annual risk of HCC of at least 5%. The study reported no difference in the sensitivity of the two approaches (annual nceMRI (71%) vs 6 monthly USS (45%); p=0.077). However, a simulated approach where annual nceMRI was added to the 6 monthly USS improved sensitivity to 84% which was significantly better than then sensitivity of 6 monthly USS.

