11.2. Description of the Statistical Methods

Statistical analysis for Primary outcome measure

Measures of diagnostic performance will be determined per round of surveillance and over the 30 months of study participation.

Diagnostic performance per round of surveillance

At each round of surveillance, the following data will be calculated and compared between USS and nceMRI.

- 1. Number and proportions of positive surveillance USS and nceMRI see section 9 for definitions of positive tests
- Number and proportions of true positive (TP) and false positive (FP) USS and nceMRI. As each positive test will be followed by a full contrast enhanced MRI, TP and FP tests per round of surveillance will be calculated
- 3. Positive predictive value (PPV) of USS and nceMRI

Diagnostic performance for the overall study period of 30 months

For the purpose of this analysis, each USS and nceMRI scan for each participant completing the study will be assigned only one of the 4 possible diagnostic categories of: true positive (TP) or false positive (FP), true negative (TN) and false negative (FN). The sum of TP, FP, TN and FN in this analysis will therefore be equal to the total number of participants completing the study. TP and FP will be determined at each visit as described above. TN and FN will be determined at the end of the study when participants undergo the reference standard ceMRI as part of the study protocol. FN results will also include those cases that present with HCC during the study without a prior positive test (interval cancers) or cases where both USS and nceMRI are negative tests but a ceMRI scan is triggered by an AFP>20. Cases that are initially FP may subsequently change diagnostic category. For this analysis, the diagnostic category which is applicable at the end of the study will be used. For example, if a finding initially classed as an FP develops into an HCC that was correctly identified by the surveillance tests, then the diagnostic test will be counted as a TP for this analysis.

Sensitivity and specificity estimates will be calculated separately for nceMRI and USS and compared. Statistical significance of the observed differences in sensitivity/specificity will be evaluated using the McNemar's test of paired proportions, with a two-tailed P-value <0.05 used as the significance criteria.

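### Section 11.3 names 200 controls as enough in most scenarios, but Table 2 requires 244 for the only specificity pair the text assumes, and its 98%/95% cell of 2 cannot be right

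*Protocol*

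**What the plan says.** Section 11.3 of the protocol bases the sample size on McNemar's test at 90% power and 5% type 1 error. Section 11.2 makes the planned comparison two-sided: "McNemar's test of paired proportions, with a two-tailed P-value <0.05 used as the significance criteria".

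For specificity, the text of 11.3 assumes a single pair, "nceMRI and USS specificity of 80%⁴³ and 90%¹⁸ respectively", and then concludes that "in most scenarios, 50 HCCs and 200 controls would be sufficient to identify a difference in sensitivity/specificity".

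Table 2, directly below, gives these minimum numbers for specificity (NA marks equal values):

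| nceMRI | USS 90% | USS 95% | USS 98% |
|---|---|---|---|
| 80% | 244 | 96 | 61 |
| 90% | NA | 530 | 173 |
| 98% | 173 | 2 | NA |

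For the yield of the cohort, 11.3 expects that the chosen risk threshold "would give rise to 50 HCCs plus ~250-300 controls with liver cirrhosis and no HCC". The enrolment target in the lay summary and synopsis is 300. Section 9.13 says that withdrawals are not replaced because the calculation already covers attrition. Section 5.4 reports a Korean study in which pre-contrast MRI sequences had "similar specificity (98% vs 95%) to USS".

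**The concern.** Two figures in 11.3 do not fit the rest of the section.

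1. The control number offered as sufficient falls below the table's own requirement for the one specificity pair that the text assumes. A reader who takes 200 as the target would believe that the specificity comparison has 90% power when it has less.
2. The 98%/95% cell is out of line with its neighbours. The table asks for 530 participants for a 5-point difference (90% vs 95%) and 173 for an 8-point difference (90% vs 98%), yet 2 for a 3-point difference. The same pair of values is reported in 5.4 from a study whose MRI protocol is described there as similar to this one. Read at face value, the cell says that a difference of that size could hardly be missed.

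Specificity is part of the primary objective, so these numbers bear on how a non-significant specificity result could be interpreted.

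**Working it through.** **Inputs.** Two-sided alpha 0.05 (11.2), power 90% (11.3), and the pairs of Table 2. The correlation between the two tests is not stated; call it r.

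**Formula** (McNemar, normal approximation), for specificities p1 and p2:

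- c = r × √[p1(1−p1) p2(1−p2)]
- p10 = p1(1−p2) − c and p01 = p2(1−p1) − c
- s = p10 + p01 and d = |p1 − p2|
- n = [1.96√s + 1.2816√(s − d²)]² / d², rounded up
- power at N = Φ{[d√N − 1.96√s] / √(s − d²)}

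**Reproducing Table 2.** With r = 0.1 the formula returns 15 of the 16 numeric cells exactly:

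- sensitivity: 31, 54, 116, 21, 30, 50, 14, 19, 27
- specificity: 244, 96, 61, 530, 173, 173

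The value 0.1 is therefore inferred from the table, not read from the protocol.

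**The assumed pair, 80% vs 90%.**

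- c = 0.1 × 0.12 = 0.012; p10 = 0.080 − 0.012 = 0.068; p01 = 0.180 − 0.012 = 0.168
- s = 0.236, d = 0.10, √s = 0.4858, √(s − d²) = 0.4754
- n = (0.9522 + 0.6093)² / 0.01 = 243.8, so 244, as printed
- power at 200 = Φ[(1.4142 − 0.9522)/0.4754] = Φ(0.972) = 83%

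**Margin at the expected number.** 300 − 50 = 250 controls, which is 6 above 244, or 6/250 = 2.4%. The protocol gives no loss rate, so the losses below are illustrative.

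| Evaluable controls | Power, 80% vs 90% (r = 0.1) |
|---|---|
| 250 (no loss) | 91% |
| about 237 (5% loss) | 89% |
| 225 (10% loss) | 88% |
| 200 | 83% |

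**The 98%/95% cell.**

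- c = 0.1 × 0.03051 = 0.00305; p10 = 0.0490 − 0.00305 = 0.04595; p01 = 0.0190 − 0.00305 = 0.01595
- s = 0.0619, d = 0.03, √s = 0.2488, √(s − d²) = 0.2470
- n = (0.4876 + 0.3165)² / 0.0009 = 718.5, so 719
- other correlations: 790 at r = 0, 648 at 0.2, 576 at 0.3; at the largest attainable r, about 0.62, n is still about 347
- power at r = 0.1: about 40% at 200 controls, 48% at 250, 55% at 300

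A requirement of 2 is impossible whatever the correlation. With two participants the McNemar statistic is at most 2²/2 = 2.0, below the critical value of 3.84.

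**Sensitivity to the correlation.** Under independence the 80% vs 90% cell becomes 269.01, so 270 controls, and the 80% vs 50% sensitivity cell becomes 54.1, so 55 HCCs.

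**The case against.** Four points on the other side deserve weight.

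- **The sentence is qualified.** It speaks of most scenarios, and by count that is true. At 50 HCCs, 7 of 9 sensitivity cells are met. At 200 controls, 5 of 7 specificity cells are met as printed, and 4 of 7 if the cell of 2 becomes 719. Table 2 also prints 244 openly. This stands. What remains is that the exception is the one specificity pair the text adopts.
- **200 is not the expected number.** Section 11.3 goes on to expect about 250 to 300 controls, and 250 gives about 91% power. A reader might infer that the study as designed is underpowered for specificity. The documents do not support that: the shortfall exists at 200, not at the number expected before losses. What remains is the margin of 6. Section 9.13 relies on an attrition allowance that 11.3 does not show. Section 11.8 limits the final analysis to participants with a baseline visit, visit 6 and a contrast-enhanced MRI. It does speak of replacing those who fall short, but 9.13 rules out replacing withdrawals, so replacement cannot be counted on.
- **The 2 may be a reading fault.** Digits can be lost when a PDF is converted, and other parts of the text were damaged. The other 15 numeric cells came through intact, but the text alone cannot settle it. It would be too strong to say that the sponsor's calculation gave 2.
- **98% vs 95% is not a planning target.** Section 5.4 calls those values similar, and the planning assumption runs the other way, with nceMRI the less specific test. A reader might infer that the study set out to detect that difference; nothing in the protocol says so. The point is only that the table should not present it as detectable.

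**Conclusion.** The point holds in limited form. For the assumed 80% vs 90% specificities, the 200 controls named in 11.3 fall 44 short of Table 2's requirement, and power is about 83% instead of 90%. The mismatch between 200 and 244 needs no outside input; the 83% rests on the inferred correlation of 0.1. At the expected 250 controls the requirement is met, but any loss above 2.4% takes the number below 244. Illustrative losses of 5% and 10% cost only a little power (89% and 88%), so the practical effect is modest.

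The 98%/95% cell cannot be 2. Its correct value is about 719 at a correlation of 0.1, with 576 to 790 for correlations of 0.3 to 0. This part is conditional on the printed protocol really showing 2; if it shows another number, the first part is unaffected. On any attainable correlation the requirement (at least about 347) exceeds the whole planned enrolment of 300, so this difference is not detectable with 90% power here.

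**What to change.** In section 11.3:

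1. Replace the figure of 200 controls with the 244 evaluable HCC-free participants that Table 2 requires for the assumed pair. Alternatively, keep 200 and state the power there (83%) together with the power at the evaluable number expected after losses. Either way, show the attrition allowance that 9.13 refers to.
2. Check the nceMRI 98% / USS 95% cell against the original calculation and correct it (about 719 at a correlation of 0.1). Note that a difference of this size cannot be detected with 90% power in this study.
3. Have the sponsor confirm and state the within-pair correlation used, apparently 0.1. Under independence the two central cells become 55 HCCs (80% vs 50% sensitivity) and 270 controls (80% vs 90% specificity).

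The cost is a few corrected figures and sentences in one section. The correction itself changes no procedure or analysis and needs no extra patients.

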3. SYNOPSIS

51 511101 515				
Study Title	Abbreviated Magnetic Resonance Imaging vs ultrasound surveillance for liver cancer detection in people at high risk of developing liver cancer			
Internal ref. no. / short title	AMULET			
Study registration	NCT06658782			
Sponsor	University of Oxford Research Governance, Ethics & Assurance, [name] Email: [contact]			
Funder	National Institute	of Health Research and Medical	Research Council	
Study Design	Prospective cohor	t study		
Study Participants	People with cirrho	osis and high risk of Hepatocellula	ar cancer (HCC)	
Sample Size	300			
Planned Study Period	Duration of an individual participant's involvement: 30 months 1 st October 2024 – 30 th April 2039 (including 10 years passive follow up) No additional funding is required as we are only accessing records during the passive follow up phase.			
Planned Recruitment period	Recruitment start date: 1 st November 2024 Recruitment end date: 30 th April 2026			
		Outcome Measures	Timepoint(s)	
Primary Objective To evaluate the diagnostic performance of non-contrast enhanced MRI (nceMRI) and ultrasound scans (USS) as surveillance tools for the diagnosis of hepatocellular cancer (HCC).		True positive tests for HCC per round of surveillance False positive tests for HCC per round of surveillance Positive predictive value for HCC per round of surveillance True negative tests for HCC over the 30 months of surveillance False negative tests for HCC over the 30 months of surveillance Sensitivity and specificity of nceMRI and USS for HCC over 30 months of surveillance	Per round of surveillance analysis will be done for each visit: Baseline, visits 2, 3, 4, 5 and 6 For the 30 months of surveillance, analysis will be done for the entire 30 months of surveillance	
Secondary objectives				
To determine the stage and size of HCC at diagnosis and the number of indeterminate lesions detected		Numbers of HCC detected by nceMRI and USS at a very	At each 6 monthly surveillance round	

To determine the proportion of patients that receive treatment with curative intent	the Barcelona Clinic Liver Cancer staging system. The number and size of HCC tumours per participant with HCC The number of new indeterminate lesions identified at each surveillance round Proportion of participants diagnosed with HCC who go	At any time point an HCC is diagnosed, the analysis

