9.13. Early Discontinuation/Withdrawal of Participants

During the course of the study a participant may choose to withdraw early from the study at any time. This may happen for several reasons, including but not limited to:

- The occurrence of what the participant perceives as an intolerable AE.
- Inability to comply with study procedures
- Participant decision

Participants may choose to stop study assessments but may remain on study follow-up.

Participants may also withdraw their consent, meaning that they wish to withdraw from the study completely. In the case of withdrawal before completing the 30 months of study participation and without completing the 6 research visits, the following options for a tiered withdrawal from the study will be available to participants:

 Participants may withdraw from further research visits, and further communication but allow the study team to continue to access their medical records and any relevant hospital data that is recorded as part of routine standard of care; e.g., scans, blood results and disease progression data etc.

- 2) Participants can withdraw from the study but permit data obtained up until the point of withdrawal to be retained for use in the study analysis. No further data would be collected after withdrawal.
- 3) Participants can withdraw completely from the study and withdraw the data collected up until the point of withdrawal. The data already collected would not be used in the final study analysis.

In addition, the Investigator may discontinue a participant from the study MRI procedures at any time if the Investigator considers it necessary for any reason including, but not limited to:

- Pregnancy
- Ineligibility (either arising during the study or retrospectively having been overlooked at screening)
- Significant protocol deviation
- Significant non-compliance with the study requirements Clinical decision (e.g. patient no longer suitable for ongoing surveillance)

Participants who withdraw will not be replaced as the sample calculation already allows for attrition.

The type of withdrawal and reason for withdrawal will be recorded in the CRF.

If the participant is withdrawn due to disease progression or an adverse event, the Investigator will arrange for follow-up visits or telephone calls until the adverse event has resolved or the participants condition optimised.

Procedures to minimise attrition

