11.7. The Level of Statistical Significance

Statistical significance will be set at p<0.05.

11.8. Procedure for Accounting for Missing, Unused, and Spurious Data.

Participants must attend the baseline and last visit (v6) and have at least one ceMRI (after a positive surveillance test, or as per protocol at the end of the study period) in order to be included in the final analysis. Participants who do not meet this will be removed and replaced for the purposes of the statistical analysis. All data from participants that fulfil this criterion will be used and analysed using intention to diagnose methods. This is to ensure that cases where a participant completes one surveillance test but not the other at a particular visit are still included. The diagnostic category of the missed test will be determined according to the diagnosis on that visit and the final diagnosis at the end of the study. In cases of HCC diagnosis, the missed test will be assigned as FN. In cases of FP results on the surveillance test performed at that visit, the missed test will also be assigned as FP.

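### Section 11.3 needs 50 HCCs and expects exactly 50, with no visible allowance for attrition or for 30-month follow-up, and sections 9.13, 11.4 and 11.8 disagree on replacement and on who is analysed

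*Protocol*

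**What the plan says.** Section 11.3 sizes the study with McNemar's test at 90% power and 5% type 1 error. Table 2 gives the minimum number of HCCs for nine pairs of sensitivities (nceMRI 70, 80 or 90%; USS 30, 40 or 50%). The section concludes that "in most scenarios, 50 HCCs and 200 controls would be sufficient to identify a difference in sensitivity/specificity". It then states the expected yield: selecting on a 3-year risk above 9% "would give rise to 50 HCCs plus ~250-300 controls with liver cirrhosis and no HCC". Section 9.4 describes the aMAP percentage as a risk over the next 3 years.

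The Synopsis and Lay Summary set enrolment at 300, and section 7 sets surveillance at six rounds over 30 months. The Synopsis also gives "Recruitment end date: 30 th April 2026".

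Three sections deal with losses:

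- Section 9.13: "Participants who withdraw will not be replaced as the sample calculation already allows for attrition".
- Section 11.8, on people who lack the baseline visit, visit 6 or any ceMRI: "Participants who do not meet this will be removed and replaced for the purposes of the statistical analysis".
- Section 11.4 puts every registered participant in the analysis.

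**The concern.** The number of HCCs drives the sensitivity comparison. The number required and the number expected are both 50, so any loss of HCCs takes the 80% versus 50% pair, whose Table 2 entry is exactly 50, below its stated power. Three features of the text point to fewer than 50: the yield refers to 300-350 people when 300 are enrolled, the only time horizon in the yield sentence is 3 years when follow-up is 2.5 years, and no attrition rate is given although section 9.13 relies on one.

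The sections on losses also cannot all be followed. They determine whether someone who leaves is replaced and whether that person's data enter the primary analysis.

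**Working it through.** **Inputs.** McNemar test, power 90%, type 1 error 5% (section 11.3), two-sided (section 11.2: "with a two-tailed P-value <0.05 used as the significance criteria"). Required: 50 HCCs and 200 controls. Expected: 50 HCCs and 250-300 controls. Enrolled: 300. Follow-up: 2.5 years. Not in the protocol, so assumed here: the within-pair correlation, the period over which the 50 HCCs accrue, and any attrition rate.

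**Step 1: reproduce Table 2.** The formula is

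n = [1.960·√pd + 1.2816·√(pd − d²)]² / d²,

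where pd is the proportion of discordant pairs and d the difference in sensitivity. For 80% versus 50% with correlation 0.1, the covariance is 0.1·√(0.8·0.2·0.5·0.5) = 0.02. The discordant proportions are 0.8·0.5 − 0.02 = 0.38 and 0.5·0.2 − 0.02 = 0.08, so pd = 0.46 and d = 0.30. Then

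n = [1.960·0.6782 + 1.2816·0.6083]² / 0.09 = 49.4, rounded up to 50.

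The same correlation returns all nine sensitivity entries exactly (31, 54, 116, 21, 30, 50, 14, 19, 27). Independence would give 55 for this pair. The correlation of 0.1 is therefore inferred, but it matches the sponsor's sensitivity table.

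**Step 2: yield for 300 people over 30 months.** If the 50 HCCs accrue over 3 years, the implied 3-year risk is 50/300 = 16.7% or 50/350 = 14.3%.

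| Denominator | Linear | Constant hazard |
|---|---|---|
| 300 | 300·0.1667·2.5/3 = 41.7 | 300·[1 − (1 − 0.1667)^(2.5/3)] = 42.3 |
| 350 | 300·0.1429·2.5/3 = 35.7 | 300·[1 − (1 − 0.1429)^(2.5/3)] = 36.2 |

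This is about 36-42 HCCs before any losses, which is 8-14 short of 50. With the 300 denominator, the horizon alone gives about 42. The lower end also reflects the 350 denominator.

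**Step 3: power at that yield.** Power = Φ{[d·√n − 1.960·√pd] / √(pd − d²)}. For 80% versus 50% at n = 42: (0.30·6.481 − 1.329)/0.6083 = 1.01, which is 84%.

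| nceMRI vs USS | Table 2 minimum | Power at 50 | at 42 | at 36 |
|---|---|---|---|---|
| 70 vs 30 | 31 | 99% | 97% | 94% |
| 70 vs 40 | 54 | 88% | 81% | 75% |
| 70 vs 50 | 116 | 56% | 49% | 43% |
| 80 vs 30 | 21 | >99% | >99% | >99% |
| 80 vs 40 | 30 | 99% | 98% | 95% |
| 80 vs 50 | 50 | 90% | 84% | 78% |
| 90 vs 30 | 14 | >99% | >99% | >99% |
| 90 vs 40 | 19 | >99% | >99% | >99% |
| 90 vs 50 | 27 | >99% | 99% | 97% |

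Seven pairs reach 90% at 50 HCCs and six do at 36-42. The pair lost is 80% versus 50%.

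**Step 4: attrition (assumed 15%).** Spread evenly over the 30 months, with HCCs found before dropout kept, the yield is about 33-39 and power at 80% versus 50% about 74-82%. If every loss occurred on day 0, the yield would be 36.2·0.85 = 31 to 42.3·0.85 = 36. The six pairs still have at least 90% power at 31.

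**Step 5: timing of replacement.** Day 900 after a first enrolment on 1 November 2024 is 20 April 2027, about a year after recruitment closes.

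**The case against.** The strongest reply is that the 3-year accrual is not stated. The yield sentence uses the 3-year risk as a selection threshold, and Figure 4, which would show the basis of the 50, is not available. This stands: 36-42 is conditional on the inference.

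Enrolment of 300 also exceeds the stated requirement of 50 + 200 = 250, and controls have slack of 50-100 (250-300 expected against 200 needed). That slack may be what section 9.13 means. So a reader might call its attrition statement false, but the text supports only a narrower criticism: no allowance is visible for HCCs, and spare controls do not help the sensitivity comparison.

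Several sources could raise the yield: HCC already present at baseline, participants with previously treated HCC (eligible without the aMAP threshold), and LI-RADS 4 lesions counted as HCC on the end-of-study ceMRI. They could offset part of the gap. The protocol quantifies none of them, so they cannot be credited either.

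A reader might also infer that the study is underpowered overall. The protocol claims sufficiency only in most scenarios, and six of nine pairs still meet 90%. The 70% versus 40% pair was already at 88% with 50 HCCs, so only its fall to 75-81% belongs to this point.

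Finally, replacement is not impossible in every case. A withdrawal, death or transplant during the 18-month recruitment period is known at once and could be replaced in time. Late losses, such as a visit 6 missed from about April 2027, could not.

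**Conclusion.** The point holds in a limited form. Without any assumption, section 11.3 has no margin on HCCs and shows no attrition factor, its yield refers to 300-350 people against 300 enrolled, and sections 9.13, 11.4 and 11.8 contradict one another.

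The size of the shortfall is conditional. If the 50 is a sum of 3-year risks, 300 people over 30 months give about 36-42 HCCs before losses. Power falls from 90% to 78-84% at 80% versus 50%, and from 88% to 75-81% at 70% versus 40%. These power figures rest on a correlation of 0.1, which the protocol does not state but which reproduces its sensitivity table. Attrition would lower the yield further and the unquantified HCC sources would raise it. The documents do not support a conclusion that the study cannot answer its primary question: the effect is moderate and falls on the smaller sensitivity differences.

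**What to change.** - **Section 11.3:** state the expected number of HCCs for 300 people over 30 months, the accrual horizon behind it, an explicit attrition figure, and the power this gives for each sensitivity pair. If baseline, previously treated or end-of-study LI-RADS 4 cases are counted on, say how many are expected.
- **Section 9.13:** correct the attrition statement, or show the allowance for HCCs.
- **Section 11.8:** delete the promise of replacement, so that it agrees with 9.13.
- **Sections 11.4 and 11.8:** give one definition of who is analysed.

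The cost is protocol wording, one recalculation and a somewhat less favourable stated power. No extra patients are needed.
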